One of the most frequently used alternative therapies is herbal medicine that act as anti-ROS agents preventing DNA damage has been used alongside conventional treatment regimens (Li et al, 2016). One of the agents that receives particular strong interest is coffee. Coffee is considered as a major source of dietary antioxidants; some are present in the green bean, whereas others are generated during roasting. Coffee roasting, the process of the heating of green coffee beans transforming them into black coffee beans, transforms the chemical and biological properties of coffee beans (Wei et al. 2012 and Jeong et al, 2013).

Regarding oral cancer, some studies reported an association of high coffee consumption to an augmented risk of oral cancer (Bundgaard et al, 1995 and Franco et al, 1989) while others showed a clear inverse association with the risk of oral cancer (Naganuma et al, 2008 and Hildebrand et al, 2013). Recently, there have been reports of a protective effect of coffee consumption on oral cancer from two recent meta-analysis (Zhang et al, 2015 and Li et al, 2016). To our knowledge, only two studies were done to assess the effect of coffee ingredients (cafestol and kahweol) on oral squamous cell carcinoma cell lines (Chae et al, 2014 and Kotowski et al, 2015).

Due to these controversial findings concerning the effect of roasted coffee and absence of data on unprocessed (green coffee), our study aims to investigate the effect of different coffee beverage as regard apoptosis and proliferation carried out in OSCC cell lines.

Rationale for carrying out this study:

The main objective of our study was to evaluate anti proliferative and apoptotic activity of green coffee, in comparison to roasted coffee and decaffeinated coffee on cultured OSCC cell line.

PICO

Patient / Population: Human Oral squamous cell carcinoma cell line

Intervention1: Green coffee

Intervention2: Roasted coffee

Intervention3: Decaffeinated coffee

Control: no application

Outcome:

Primary outcome 1: assessment of proliferative activity OSCC cell line treated with coffee using **ELISA**.

Primary outcome 2: Assessment of apoptotic cell death of OSCC cell line treated with coffee using **RT-PCR**.

	Outcome measure	Measuring device	Measuring unit
1- Primary1	Proliferative activity	ELISA	Comparative (light absorbed) numerical value
1- Primary2	Apoptotic cell death	RT-PCR	Comparative (fold changes) numerical value

Research question

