% cytotoxicity = 1 - [means absorbance of treated cells/mean absorbance of negative control], % viability = 100 - % cytotoxicity.

Measurement of proliferative activity:

Enzyme assay (ELISA) will be used to estimate the inhibitory effect green coffee, roasted coffee, decaffeinated coffee on **Epidermal growth factor Receptor (EGFR)** protein.

Sample preparation for ELISA:

Cell lysis for cell culture samples will be carried by spinning down cells for 15 minutes at 1200 RPM. Cell pellets are washed once in cold PBS. Cells are re-suspended in Lysis Buffer to a concentration of 1.5x10⁶ cells/mL, are incubated for 1 hour at room temperature with gentle shaking. Cells are centrifuged at 200 x g for 15 minutes. The supernatant will be diluted at least 50-fold in 1X Assay Buffer (5 μ L supernatant + 245 μ L 1X Assay Buffer) for the assay.

1. Prepared biotin antibody is added to samples in different wells.

2. Then prepared Streptavidin horseradish peroxidase (HRP) solution is added after washing.

3. Tetramethylbenzidine (TMB) Solution is added to each well and incubated at room temperature. Stop Solution is added to each well. Readings will be done at 450 nm immediately

Apoptosis activity assay:

Following treatment with green coffee or roasted coffee or decaffeinated coffee for 24 h, the cells are harvested, lysed and tested with RT-PCR using specific primers to estimate the fold change of the gene expression of Caspase-3, bax, bcl-xl and p53.

7. Calculated sample size

No sample size estimation could be done, as the primary outcome is not a measured outcome.

8. Description of study sample

No sample size could be applied on cell line experiments as we generate millions of naturally randomized cells.

9. Intervention for each group

Green coffee extract will be introduced to the 1st group, while roasted coffee will be added to the 2nd group. The 3rd group will be treated with decaffeinated coffee.

10. Outcomes

Apoptosis (Gene expression of Caspase – 3, EGFR).

Prioritization of Outcome	Outcome	Method of measurement	Measuring unit
Primary1	EGFR expression using ELISA	Robonek P2000 ELISA reader	IC 50 µg / ml
Primary2	Caspase-3, bax, bcl-xl and p53 gene expression using RT – PCR	Rotorgene system	Fold change FLD=e-ΔΔCT

B)Assignment to intervention

This study is non-randomized.

11. Sequence generation

Sequence generation is not applied on cell line experiments.

12. Allocation concealment

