Allocation concealment is not applied on cell line experiments.

13. Implementation

Implementation is not applied on cell line experiments.

C) Blinding

14. Blinding

Blinding is not applied on cell line experiments.

D) Statistical methods

Data will be analyzed using IBM SPSS advanced statistics (Statistical Package for Social Sciences), version 21 (SPSS Inc., Chicago, IL). Numerical data will be described as mean and standard deviation or median and range. Categorical data will be described as numbers and percentages.

IV- References:

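### The fold-change formula for the second primary outcome has an undefined base 'e'; read as Euler's number it overstates every log fold change by a factor of 1.44

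*Protocol*

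**What the plan says.** The second primary outcome is listed in the Protocol section 10 table as "Caspase-3, bax, bcl-xl and p53 gene expression using RT – PCR". Its measuring unit is fold change, and the cell gives the formula "FLD=e-ΔΔCT". The raised exponent has been lost in the text at hand, so this is read as e to the power -ΔΔCT.

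This is the only fold-change formula in the protocol. The outcome table under the PICO heading gives the unit only as "Comparative (fold changes) numerical value". The paragraph headed Apoptosis activity assay says that cells will be "tested with RT-PCR using specific primers to estimate the fold change of the gene expression of Caspase-3, bax, bcl-xl and p53". None of these places says what 'e' stands for or gives an amplification efficiency or a base.

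Section D, Statistical methods, plans that "Numerical data will be described as mean and standard deviation or median and range". It does not mention the formula.

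**The concern.** In a formula of this kind the base is the factor by which template multiplies in one PCR cycle. As the base of a power, the letter e ordinarily means Euler's number, 2.718. That is more than a doubling per cycle, which PCR cannot deliver. An analyst who follows the cell literally would report fold changes that lie too far from 1, both for genes that go up and for genes that go down.

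What is at stake is the size of the reported effect. Fold change is the stated unit of a primary outcome, and section D plans to describe numerical data by their mean and SD or median and range. The magnitude is therefore itself the planned descriptive result.

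**Working it through.** **Inputs.** From the protocol: the formula in the section 10 table and the summaries named in section D. The protocol states no fold change, ΔΔCT or efficiency, so there is no figure of its own to reproduce. Assumed for illustration: ΔΔCT values from -3 to +3, and amplification factors of 1.8 and 1.9. The ceiling of 2 is not a figure in the protocol; it follows from doubling per cycle.

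**Step 1: admissible base.** Fold change = b^(-ΔΔCT), with b = 1 + E and efficiency E between 0 and 1, so b lies between 1 and 2. Setting b = 2.718 implies E = 1.718, or 171.8%, above the 100% ceiling.

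**Step 2: single values.**

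| ΔΔCT | Base 2.718 | Base 2 | Ratio |
|---|---|---|---|
| -1 | 2.72 | 2.00 | 1.36 |
| -2 | 7.39 | 4.00 | 1.85 |
| -3 | 20.09 | 8.00 | 2.51 |
| +1 | 0.368 | 0.500 | 0.74 |
| +2 | 0.135 | 0.250 | 0.54 |
| +3 | 0.050 | 0.125 | 0.40 |

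On the natural-log scale the fold change is -ΔΔCT with Euler's number and -ΔΔCT × ln 2 with base 2. The ratio is 1/ln 2 = 1/0.693 = 1.44 at every non-zero ΔΔCT.

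**Step 3: the planned summaries, for three assumed replicates.**

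| ΔΔCT of replicates | Summary | Base 2.718 | Base 2 |
|---|---|---|---|
| -1, -2, -3 | Mean (SD) | 10.06 (8.99) | 4.67 (3.06) |
| | Median (range) | 7.39 (2.72 to 20.09) | 4.00 (2.00 to 8.00) |
| +1, +2, +3 | Mean (SD) | 0.184 (0.165) | 0.292 (0.191) |
| | Median (range) | 0.135 (0.050 to 0.368) | 0.250 (0.125 to 0.500) |

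**Step 4: can values be converted afterwards?** Since (e^(-d))^(ln 2) = 2^(-d), an individual value converts exactly when raised to the power 0.693: 7.39 becomes 4.00 and 0.135 becomes 0.25. The minimum, the maximum and the median of an odd number of values convert the same way, because the transformation is monotone. The mean and SD do not: 10.06^0.693 = 4.96, not 4.67, and 8.99^0.693 = 4.58, not 3.06.

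**Step 5: the other reading.** If 'e' is an amplification factor, nothing is exaggerated. At ΔΔCT = -2, assumed factors of 1.8, 1.9 and 2.0 give 1.8² = 3.24, 1.9² = 3.61 and 2² = 4.00.

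**The case against.** The strongest reply is that 'e' may never have meant Euler's number. It stands inside a ΔΔCT formula for RT-PCR, where an amplification factor is a natural reading, and nowhere does the protocol describe a natural exponential. On that reading the formula is valid in form. The efficiency of each gene assay is also the kind of detail that may properly sit in a laboratory procedure or in an analysis plan that is not at hand. This stands. It limits the error to the Euler reading and rules out an unconditional instruction to use base 2: if the true factor were 1.8, base 2 would report 4.00 instead of 3.24 at ΔΔCT = -2.

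The second reply is that the text was read from a PDF. The exponent formatting is gone, and a 2 misread as an e cannot be excluded. Against this, the same section keeps the superscript in the cell concentration for the ELISA lysate, and the Δ symbols survive in the formula itself. The printed character is the best evidence available, but the doubt remains until someone looks at the original.

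The third reply is that little depends on it. This also stands. The base is a fixed monotone transformation, so the direction of an effect and the ranking of values for a gene do not change, nor does an analysis on the ΔΔCT scale. The protocol ties no threshold or decision rule to the formula.

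A reader might infer more, namely that the formula gives no usable fold change however 'e' is read. The protocol does not support that. Euler's number gives a definite value on an inflated scale, and an amplification factor gives a valid formula that still needs its definition.

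**Conclusion.** The point holds in a limited form and is minor. The only formula printed for the second primary outcome leaves its base undefined, and on the ordinary reading of the symbol it gives wrong magnitudes: log fold changes too large by a factor of 1.44, carried into the planned summaries. If 'e' was meant as an amplification factor, only a definition is missing.

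The conclusion rests on three things: that the source really prints e, that the lost formatting was an exponent, and that template at most doubles per cycle. The 1.44 holds for any non-zero ΔΔCT relative to base 2; the means, SDs, medians and ranges in the working depend on assumed replicates.

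A reader might also infer that reported results are wrong or that the comparison of the coffees is compromised. The protocol contains no results and does not show which base was or will be used, so neither inference is supported.

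**What to change.** 1. Check the character in the original PDF. If it prints 2, the point falls.
2. If it prints e, replace the formula in the section 10 table with: fold change = 2^(-ΔΔCT).
3. If an efficiency-corrected formula was intended, keep the form instead, define 'e' as the per-cycle amplification factor (at most 2), and state how it is obtained for each of the four genes.
4. If any values have already been computed with Euler's number and base 2 is the intended formula, raise each individual value to the power ln 2 = 0.693 and then recompute the mean and SD. Do not convert a mean or SD directly. Individual values, the minimum, the maximum and an odd-sample median can be converted as they stand.

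The cost is one table cell, or one cell and a sentence if 'e' is defined. The base-2 correction needs no laboratory work.

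### Random assignment is set aside as inapplicable to cell lines, and no rule makes the four groups share a plate or run, so position, order or run could be confounded with coffee type

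*Protocol*

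**What the plan says.** Section B (Assignment to intervention) opens with "This study is non-randomized". Item 11 then says "Sequence generation is not applied on cell line experiments". Items 12 to 14 dismiss allocation concealment, implementation and blinding in the same way.

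The nearest thing to a reason is in item 8, which gives up on a sample size "as we generate millions of naturally randomized cells". Item 9 assigns treatment by group: "Green coffee extract will be introduced to the 1st group, while roasted coffee will be added to the 2nd group", with decaffeinated coffee for the third. The PICO list adds an untreated control.

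The outcomes are expressed in three ways:

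- **MTT (viability):** cytotoxicity is one minus the ratio "means absorbance of treated cells/mean absorbance of negative control".
- **RT-PCR (primary outcome 2):** "the cells are harvested, lysed and tested with RT-PCR using specific primers to estimate the fold change of the gene expression" of four genes, computed according to the item 10 table as "FLD=e-ΔΔCT".
- **ELISA for EGFR (primary outcome 1):** the PICO table gives the unit as "Comparative (light absorbed) numerical value", while the item 10 table gives an IC50 in µg/ml. No ratio to control is written for this assay.

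The Methods mention a 96-well plate. They do not say how many plates or runs there are, which groups each holds, or in what order samples are handled.

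**The concern.** Item 11 treats randomisation as something that cannot apply to cell lines, but it can. The units that receive a coffee type are wells or cultures, and these yield the lysates and RNA samples that are measured. Each can be given a random position and a random place in the processing order. The naturally randomised cells of item 8 do not help, because no single cell is allotted to a coffee type; all cells in a well get the same one.

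The main objective is to compare green coffee with roasted and decaffeinated coffee. If one coffee sits at one side of a plate, is always processed last, or is run on another day, its apparent effect mixes the extract with that position, order or run. No later analysis can separate the two when they coincide fully. That is why this is a matter for the Protocol and cannot be left to an analysis plan.

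**Working it through.** The Protocol states no sample size, replicate number or expected effect, so there is no figure to reproduce. The check asks which offsets would survive the planned calculations, how large they might be under stated assumptions, and whether all groups fit together.

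**1. What cancels**

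- *MTT.* If a plate multiplies every absorbance by k, the ratio is (k × treated)/(k × control) = treated/control. A shared proportional offset disappears. One that differs between treated and control wells does not.
- *RT-PCR.* ΔCT = CT(target) − CT(reference) and ΔΔCT = ΔCT(coffee) − ΔCT(control). An offset common to target and reference cancels in ΔCT, even across runs. An offset in ΔCT shared by coffee and control cancels in ΔΔCT, giving a factor e^0 = 1.00. Only an offset that is specific to the target (or the reference) and also differs between groups survives.
- *ELISA.* Under the light-absorbed unit no control ratio is written, so a plate offset would stay in comparisons across plates. An IC50 would normally be read relative to the uninhibited response, so a proportional offset shared with the control would cancel. The two units conflict, and the text does not settle which applies.

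**2. ELISA position effect (illustration; all inputs assumed)**

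Assume 3 wells per group, so 4 × 3 = 12 wells, with one column per group in adjacent columns. Assume absorbance changes linearly by G across 12 columns, that is by G/11 per column. All extracts are taken as inert.

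| Difference between group means | Formula | G = 5% | G = 10% | G = 20% |
|---|---|---|---|---|
| First and last group | 3G/11 = 0.273G | 1.4% | 2.7% | 5.5% |
| Adjacent groups | G/11 = 0.091G | 0.5% | 0.9% | 1.8% |
| Random positions in the same 12 wells: mean | 0 | 0 | 0 | 0 |
| Random positions in the same 12 wells: SD | 0.087G | 0.4% | 0.9% | 1.7% |

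For the SD, the column positions are 0, 1/11, 2/11 and 3/11, three wells each. Their variance is S² = [3 × (2.25 + 0.25 + 0.25 + 2.25)/11]/121 = 0.01127, and sqrt(2 × 0.01127/3) = 0.087.

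**3. RT-PCR offset (illustration)**

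Suppose an offset of 0.25, 0.5 or 1.0 in ΔCT survives between a coffee group and control. It changes the fold change of an inert extract by a factor of e^0.25 = 1.28, e^0.5 = 1.65 or e^1.0 = 2.72 with the printed base e. With base 2 as a sensitivity check the factors are 1.19, 1.41 and 2.00. Nothing in the Protocol says how likely such offsets are.

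**4. Can all groups share a plate or run?**

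- *MTT:* 3 coffees × 5 concentrations + 1 control = 16 conditions. At 5 wells each this is 80 wells, leaving 96 − 80 = 16 for blanks. On the 6 × 10 = 60 interior wells, 3 each takes 48 and leaves 12.
- *RT-PCR,* one sample per group and one assumed reference gene: 4 × (4 + 1) = 20 reactions, or 60 in triplicate. Split by gene, a run needs 4 × 2 = 8, or 24 in triplicate.
- *ELISA:* 12 wells under the assumption above.

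Sharing is feasible for every assay under these assumptions.

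**The case against.** The strongest reply is that the Protocol is silent on layout and does not state a bad one. It uses one cell line, cultures it with and without extract, mentions a single plate format and divides by one negative-control mean. A fixed plate map holding all four groups would fit that wording. This stands: confounding is a possibility, not something the text shows. A plate format is still not a rule that groups share a plate, and it does not govern the lysates and RNA behind the two primary outcomes.

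A second reply is that randomising is only one remedy. Under a pure column gradient, a fixed map with each group spanning the same columns gives a difference of exactly 0, whereas random positions leave an SD about as large as the adjacent-group offset. This also stands in part. The essential element is that groups share plates and runs; random position comes second. A fixed map protects only against the gradients it was balanced for, and it does not address processing order.

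A reader might go further and infer a large bias or a badly inflated false-positive rate. The Protocol does not support that. A first-to-last difference of 9/11 of the gradient (4.1, 8.2 or 16.4%) would need four blocks of 24 wells, which matches neither the 16 MTT conditions nor a small ELISA layout. An inflated type I error would need each coffee on its own plate and a significance test on wells. The Protocol states neither; its statistical section names only descriptive summaries.

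**Conclusion.** The point holds as a cheap improvement. Item 11 declares random assignment inapplicable to units that can be randomised, the only related reason concerns single cells, and no rule makes the groups share a plate or run. Position, processing order or run can therefore be confounded with coffee type, in the comparison that the study exists to make.

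The size of any bias is unknown. The 1.4, 2.7 and 5.5% figures rest on an assumed gradient, an assumed 3 wells per group and an assumed column layout; the RT-PCR factors rest on assumed offsets. Normalisation removes whatever is shared with the control in MTT and ΔΔCT, and whatever is common to target and reference gene in ΔCT. Primary outcome 1 is the least clearly protected, because its two stated units conflict. It does not follow that the results will be biased.

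**What to change.** Replace item 11 with wording such as:

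> Every plate and every run (culture, ELISA, RT-PCR) contains all four groups, including the untreated control. Within each plate or run, positions and processing order are assigned by a computer-generated random list, or by a layout balanced over rows and columns with groups assigned at random.

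If one RT-PCR run cannot hold all genes, split runs by gene, each with its reference gene, and not by group. Change the sentence in section B that calls the study non-randomised so that it agrees.

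The cost is a plate map and list for each plate or run, slower pipetting, and a misplaced well that is harder to notice. A run must also wait until all three extracts are ready. Randomising position and order adds no wells or reactions. One limit should be stated: with only one sample per group, random order removes systematic bias but does not average out the offset in that single comparison.
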